Appendix L Protocol Amendment History

The Protocol Amendment Summary of Changes Table for the current amendment is located directly before the Table of Contents.

Amendment 1.0: 15 November 2021

This amendment is considered to be non-substantial based on the criteria set forth in Article 10(a) of Directive 2001/20/EC of the European Parliament and the Council of the European Union because it neither significantly impacts the safety or physical/mental integrity of participants (study did not start enrolment at the time of this amendment) nor the scientific value of the study.

Overall Rationale for the Amendment:

Section # and Name	Description of Change	Brief Rationale	Substantial/Non- substantial
Sections 1.3 Schedule of Activities and 8.1.5.5 SNOT-22	Completion of SNOT-22 is restricted to participants with history of chronic sinusitis at baseline.	Some questions in the SNOT-22 questionnaire are relevant only to participants with chronic sinusitis.	Non-substantial
Section 1.3 Schedule of Activities	Completion of AIRQ TM and SNOT-22 at the IPD visit has been added.	To be consistent with the requirements for the other questionnaires.	Non-substantial
Sections 1.3 Schedule of Activities, 8.3.5 Adverse Events Based on Examinations and Tests, and 8.3.6 Adverse Events of Special Interest	The list of AESIs has been modified.	Changes made to align the protocol to the IB v5.0.	Non-substantial
Section 3 Objectives and endpoints	Total cumulative prescribed OCS up to Week 28 and Week 52 has been deleted from exploratory endpoint list.	It is included in derivation of the endpoint Mean daily SCS exposure of systemic corticosteroids (mg/day) taken for asthma reasons over 28 and 52 weeks.	Non-substantial
Section 5.4.1 Re-screening	Procedures to be performed during re-screening have been modified.	To reduce the inconvenience for participants who are rescreened.	Non-substantial
Section 6.2.6 Single Use APFS Device Malfunction	Reference to Appendix K for definition of medical device AEs, SAEs and deficiencies in medical device studies has been added as well as the corresponding appendix.	To clarify the process to be followed in case of medical device AEs, SAEs and deficiencies.	Non-substantial

Section # and Name	Description of Change	Brief Rationale	Substantial/Non- substantial
Section 6.5 Prior and Concomitant Therapy	Restrictions on background therapies (BD, short-acting β-agonists, LABA, LAMA, theophyllines) before FeNO assessment had been deleted in Table 5.	To more closely align the protocol with routine clinical practice.	Non-substantial
Section 7.1 Discontinuation of Study Intervention	Helminth parasitic infestation requiring hospitalisation has been replaced by helminth parasitic infestation not responding to anti-helminth treatment in the list of specific criteria for discontinuation.	Change made for consistency with the draft US label of tezepelumab	Non-substantial
Sections 8.1.4 Spirometry and 11 References	Reference for spirometry guidelines have been updated (Miller et al. 2005 has been replaced by Graham et al. 2019).	To use the most recent recommendations of the American Thoracic Society and European Respiratory Society.	Non-substantial
Sections 1.3 Schedule of Activities, 8.1.5.2 SGRQ, 8.1.5.3 AQLQ(S)+12, 8.1.5.4 AIRQ TM , 8.1.5.5 SNOT-22, and 8.1.5.6 PPOCS	Time windows for questionnaires have been modified or specified (±5 days as been replaced by ±2 days.	To align the time windows for all questionnaires for consistency (±2 days).	Non-substantial
Section 8.2.4.1 Weight and Height	Mention of body mass index has been added.	To clarify that body mass index will be calculated and not captured in the eCRF.	Non-substantial
Section 8.3.5 Adverse Events Based on Examinations and Tests	Guidance for management of deterioration in laboratory values, physical exams, vital signs performed as usual care during the study has been added.	To clarify that such deteriorations should be reported as AEs only if they fulfil the criteria for an SAE, DAE, or AESI.	Non-substantial
	AESI has been added as a reason to record signs and symptoms of adrenal insufficiency.	To clarify that adrenal insufficiency signs and symptoms have to be recorded if the participant experiences an adrenal crisis, now listed as AESI.	Non-substantial
Section 8.6.1 FeNO	Time window for visits post	To gain consistency with time window required for	Non-substantial

Section # and Name	Description of Change	Brief Rationale	Substantial/Non- substantial
	Visit 2 has been modified.	spirometry assessments.	
Section 9.4.1 General Considerations	Definition of composite strategy to be applied for primary endpoint and other OCS endpoints has been updated.	To gain consistency across the document.	Non-substantial
	It has been specified that safety analyses will be done based on on-treatment and/or on-study period.	To provide additional clarification.	Non-substantial
Section 9.4.3.1 Primary Endpoints	Description of final OCS derivation has been updated.	To provide additional clarification of final OCS dose derivation.	Non-substantial
Section 9.4.3.2 Secondary Endpoints	Description of the statistical model for continuous secondary endpoints has been updated.	To provide additional clarification.	Non-substantial
Throughout	Minor editorial and document formatting revisions.	Minor; therefore, have not been summarised.	Non-substantial

Abbreviations: AE = adverse event; AESI = adverse event of special interest; $AIRQ^{TM} =$ Asthma Impairment and Risk Questionnaire; APFS = accessorised pre-filled syringe; AQLQ(s)+12 = standardised Asthma Quality of Life Questionnaire for 12 years and older; BD = bronchodilator; eCRF = electronic Case Report Form; FeNO = Fractional exhaled nitric oxide; IB = Investigator Brochure; IPD = premature investigational product discontinuation; LAMA = long-lasting muscarinic antagonist; LABA = long acting BE = agonist; BE = serious adverse event; BE = Systemic Corticosteroid; BE = Serious adverse event; BE = Systemic Corticosteroid; BE = Serious adverse event; BE = Systemic Corticosteroid; BE = Serious adverse event; BE = Systemic Corticosteroid; BE = Serious adverse event; BE = Systemic Corticosteroid; BE = Serious adverse event; BE = Systemic Corticosteroid; BE = Serious adverse event; BE = Systemic Corticosteroid; BE = Serious adverse event; BE = Systemic Corticosteroid; BE = Serious adverse event; BE = Systemic Corticosteroid; BE = Serious adverse event; BE = Systemic Corticosteroid; BE = Serious adverse event; BE = Systemic Corticosteroid; BE = Serious adverse event; BE = Systemic Corticosteroid; BE = Serious adverse event; BE = Systemic Corticosteroid; BE = Serious adverse event; BE = Systemic Corticosteroid; BE = Serious adverse event; BE = Systemic Corticosteroid; BE = Serious adverse event; BE = Systemic Corticosteroid; BE = Systemic Corticosteroid;

Appendix M Alternative Method for Hypothalamic-pituitary-adrenal Axis Evaluation

FOR USE ONLY IF TETRACOSACTIDE IS NOT REGISTERED IN YOUR COUNTRY OR WITH PERMISSION FROM LABCORP IF TETRACOSACTIDE IS NOT AVAILABLE AT YOUR SITE

First test (before reducing the maintenance OCS dose below 5 mg per day)

Sample	8–9am cortisol cortisol ^a	Action	Status
1	>350 nmol/L	Continue down-titration (2.5 mg every 4 weeks to zero)	No AI
	100–350 nmol/L	Repeat 8–9am cortisol approximately 1 week later (instead of performing ACTH stimulation test) and interpret according to sample 2 below	Indeterminate
	<100 nmol/L	Delay titration and repeat test in 3 months ^b	Complete AI

Second test - Approximately 1 week after the first test in case the first test was indeterminate

Sample	8–9am cortisol cortisol ^a	Action	Status
2	>350 nmol/L	continue down-titration (2.5 mg every 4 weeks to zero)	No AI
	≤350 nmol/L or when signs or symptoms of AI are present	If serum cortisol ≥250 nmol/L on either sample 1 or sample 2, proceed with slow titration (1 mg every 4 weeks) until the participant reaches a prednisolone / prednisone dosage of 3 mg per day and then repeat testing ^b (ie, at 2 months – see 3 rd test below)	Partial AI
		If serum cortisol <250 nmol/L on both samples 1 and 2, delay titration and repeat test in 3 months ^b (see 3 rd test below)	Complete AI

Third test - 2 or 3 months later (see Section 8.2.1)

[figure not shown]
Sample	8–9am cortisol	Action	Status
	cortisol ^a		
3	>350 nmol/L	Continue down-titration (2.5 mg every 4 weeks to zero)	No AI
	100–350 nmol/L	Repeat 8–9am cortisol approximately 1 week later and interpret according to sample 4 below	Indeterminate
	<100 nmol/L	Delay titration and repeat test in 3 months ^b	Complete AI

Fourth test - Approximately one week after the third

Sample	8–9am cortisol cortisol ^a	Action	Status
4	>350 nmol/L	Continue down-titration (2.5 mg every 4 weeks, or 1 mg every 4 weeks if signs or symptoms of AI are present)	No AI
	≤350 nmol/L or when signs or symptoms of AI are present	If serum cortisol ≥250 nmol/L on either sample 3 or sample 4, continue with slow titration (1 mg every 4 weeks) until the participant reaches a prednisolone / prednisone dosage of 1 mg per day and then repeat testing (ie, at 2 months) and discuss with endocrinologist ^b	Partial AI
		If serum cortisol <250 nmol/L on both samples 3 and 4, delay titration and discuss with endocrinologist	Complete AI

^a NB thresholds must be adjusted upward for women receiving oral oestrogen therapy as per existing protocol.

^b Participants will be educated for symptom awareness of adrenal suppression and use of steroid emergency cards.

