- 2. **Induction phase From Week 0 to 4:** After confirmation of eligibility criteria, participants will start receiving tezepelumab treatment at Visit 2/Week 0 (baseline) and should remain stable on their baseline OCS dose during this phase.
- 3. Oral corticosteroid reduction and maintenance phase From Week 4 to Week 52: Site visits will occur Q4W. Participants will reduce their dosage of OCS according to the schema defined in Table 7 for each baseline OCS dose until they reach the lowest stable OCS dose or until Week 48. The first OCS dose reduction may occur at Visit 3. OCS dose reduction may occur remotely if the scheduled dose reduction does not coincide with a site visit.

Participants will be considered as having reached the lowest stable dose when they have discontinued OCS or no further OCS reduction is possible because of loss of asthma control and/or evidence of AI (as confirmed by morning cortisol test or adrenocorticotropic hormone [ACTH] stimulation test).

Once they reach the lowest stable dose, participants will be considered in maintenance. From Week 48 to Week 52, all participants will remain on their stable daily OCS dose, except if an asthma deterioration or exacerbation occurs. No further down-titration will be allowed from Week 48 onwards.

HPA axis integrity will be evaluated for all participants who have been on 5 mg/day OCS for 4 weeks and prior to any further tapering down the OCS dose (for participants with baseline OCS doses equal to 5 mg/day, this will be assessed 4 weeks after the first dose of tezepelumab administration and before initiation of the OCS reduction and maintenance phase). A screening method with morning serum cortisol (see Section 8.2.1.1) will be done (8 to 9 am morning cortisol level), to evaluate whether the participant has normal cortisol levels or complete AI. Cortisol levels from the morning cortisol test that will be below normal range and above the complete AI range will be considered 'indeterminate' and will require additional testing (ACTH stimulation test or alternative method, as described in Appendix M).

Depending on the morning cortisol level results, the participant will continue per the following guidance:

- Cortisol levels within normal range (Table 9):
 - Participant exhibits absence of signs and/or symptoms of AI: continue OCS down-titration by 2.5 mg Q4W
 - Participant exhibits signs and/or symptoms of AI: continue OCS down-titration at a slower pace (1 mg Q4W)

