Figure 3: For normal cortisol levels with concurrent signs/symptoms of AI, OCS down-titration should continue at a slower pace (1 mg Q4W). For complete AI identified via morning cortisol testing, refer to Section 8.2.1.1 for instructions on 3-month repeat testing. For partial AI or complete AI identified via ACTH stimulation test see Section 8.2.1.2 for instructions on 2-month or 3-month repeat testing respectively.

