8.2.1.1 Morning Cortisol Test

The morning cortisol test will be done in all participants 4 weeks after reaching the 5 mg dose of OCS, and before further dose reductions. It is also done 3 months after a participant has completed a test indicating complete AI.

Serum samples for cortisol will be collected between 8 and 9 am and will be sent to a central laboratory for evaluation.

The following values will be used to define AI status for the morning cortisol test:

Table 9 Cortisol Status

AI status	SI units	Participants taking oestrogen- containing contraceptives
Normal	>350 nmol/L	>700 nmol/L
Indeterminate results	100 - 350 nmol/L	200 - 700 nmol/L
Complete AI	<100 nmol/L	<200 nmol/L

Once the results are available, the site will inform the participant of the results via telephone. For sites where tetracosactides are available, and depending on the result, the actions that will be implemented are as follows:

- If cortisol levels are within normal range and the participant does not exhibit any signs and/or symptoms of AI, the participant will continue OCS down-titration by 2.5 mg Q4W
- If cortisol levels are within normal range but the participant exhibits signs and/or symptoms of AI, then OCS down-titration should continue at a slower pace (1 mg Q4W).
- If cortisol levels are below the normal range and above the complete AI range (indeterminate result), then the participant will be instructed to maintain the current OCS dose and come back to the site within 1 week for an ACTH stimulation test (Section 8.2.1.2)
- If complete AI is confirmed, sites will inform participant that the OCS dose will remain the same without further reduction until there is evidence of recovery from the complete AI without worsening of asthma control. The morning cortisol test and associated clinical assessments (see Table 1) will be repeated 3 months later. After the repeat morning cortisol test, the site will inform the participant based on the results as follows:
 - If morning cortisol results indicate normal cortisol values, then reductions will be 2.5 mg Q4W, and the participant would subsequently move to maintenance at the OCS lowest possible dose
 - If morning cortisol results are indeterminate, then reductions will be delayed further, and the participant would return approximately 1 week later for an ACTH stimulation test:
 - o If normal result after ACTH stimulation (Table 10): reduce by 2.5 mg Q4W then move to maintenance at the lowest possible dose

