8.2.1.2 Adrenocorticotropic Hormone Stimulation Test

The tetracosactide (also known as Synacthen, Cortrosyn, or cosyntropin) ACTH stimulation test will be performed when morning cortisol levels are in the indeterminate range (for sites

where tetracosactide is not available or not registered, please see Appendix M).

Options for sourcing tetracosactide are provided below:

- Acquire Synacthen or Cortrosyn 250 mg for intravenous (IV) or intramuscular (IM) injection locally and submit invoices for reimbursement (preferred option, if possible).
- If the medication is available in your country but the site cannot directly acquire the medications, then Labcorp or AstraZeneca may arrange for delivery to the site.
- If the medication is available in your country, but delivery to the site is delayed, the site may request permission from Labcorp to use the alternative method described in Appendix M.
- Sites in countries where the medications are not registered must use the alternative method in Appendix M.

The following values will be used to define AI status for the ACTH stimulation test:

Table 10 ACTH Stimulation Status

AI status	SI units	Participants taking oestrogen- containing contraceptives
Normal	>450 nmol/L	>675 nmol/L
Indeterminate results	250 - 450 nmol/L	375 - 675 nmol/L
Complete AI	<250 nmol/L	<375 nmol/L

The sites will inform the participant of the morning cortisol results via phone call, and a visit will be scheduled within 1 week for the ACTH stimulation test.

An injection of the fast-acting ACTH stimulant will be given IV or IM. Serum samples for cortisol will be collected between 8 and 9 am and will be sent to a central laboratory for evaluation as follows: a blood sample for serum cortisol will be collected at 0 minutes (before IV or IM injection) and 30 minutes after the IV or IM injection. Peak cortisol response at 30 minutes will be selected to assess AI, and the OCS taper will follow the applicable scenario below:

• If a normal peak cortisol level is demonstrated at 30 minutes, the site will inform the participant via phone call, and the participant will continue OCS dose titration by 2.5 mg Q4W aiming for 0, and subsequently would move to maintenance at the lowest possible OCS dose

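### Appendix M omits the slower taper for participants with normal cortisol and AI symptoms at the first test, and gives them two speeds and two statuses at the second

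*Protocol*

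**What the plan says.** Protocol Section 4.1 splits a normal morning cortisol by symptoms. Without signs or symptoms of AI the taper continues at 2.5 mg every 4 weeks. With them the instruction is "Participant exhibits signs and/or symptoms of AI: continue OCS down-titration at a slower pace (1 mg Q4W". The note to Figure 3 in Section 8.2.1 agrees: "For normal cortisol levels with concurrent signs/symptoms of AI, OCS down-titration should continue at a slower pace (1 mg Q4W". Neither text is limited to particular sites.

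Section 8.2.1.1 repeats the symptom rule in an action list, but opens that list with "For sites where tetracosactides are available, and depending on the result, the actions that will be implemented are as follows" and directs other sites to Appendix M. Section 8.2.1.2 adds: "Sites in countries where the medications are not registered must use the alternative method in Appendix M".

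Appendix M then says, for cortisol above 350 nmol/L:

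- **First test:** "Continue down-titration (2.5 mg every 4 weeks to zero", status No AI, no symptom clause. The third-test row is the same.
- **Second test:** the row above 350 nmol/L again gives 2.5 mg steps to zero and No AI. The next row covers values of 350 nmol/L or less and also anyone with AI signs or symptoms. If either sample is at least 250 nmol/L, it says "proceed with slow titration (1 mg every 4 weeks) until the participant reaches a prednisolone / prednisone dosage of 3 mg per day", then retest, with status Partial AI.
- **Fourth test:** the row above 350 nmol/L does carry a symptom clause, "or 1 mg every 4 weeks if signs or symptoms of AI are present", and keeps the status No AI. The next row is again entered on symptoms and gives Partial AI with a retest.

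Footnote b of Appendix M, attached to Partial and Complete AI actions, reads: "Participants will be educated for symptom awareness of adrenal suppression and use of steroid emergency cards". The No AI rows do not carry it.

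**The concern.** Sites without tetracosactide work from Appendix M, and its first-test row gives the faster taper to a participant for whom Section 4.1 prescribes the slower one. At the second test the table gives two answers for the same participant and does not say which row takes precedence.

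The first stake is patient safety. A participant already showing AI symptoms could lose the remaining 5 mg of steroid in 4 weeks. At the second test the choice of row also decides whether a repeat cortisol follows at 3 mg/day and whether the participant receives emergency-card education, which Section 8.2.1.3 and footnote b tie to partial or complete AI. Under Section 8.3.5, AI symptoms are recorded only if they are an SAE, DAE or AESI, so a misrouted participant may not show up in the adverse event data.

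The second stake is analysis. SAP 4.2.14.2 tabulates normal, partial and complete AI from the repeated morning cortisol, and SAP 4.2.1.7 uses AI status at 5 mg as a Week 52 subgroup. Neither says how to classify this case. The speed of the final taper can also decide whether 0 mg is reached in time for the Week 28 discontinuation endpoint.

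**Working it through.** The plan gives no figure of its own on this point, so there is none to reproduce. The check has three parts.

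**1. Which rows a result satisfies.** Appendix M's rows were treated as logical conditions and tried on example values.

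| Test | Result | Symptoms | Rows satisfied |
|---|---|---|---|
| First | > 350 | no or yes | 2.5 mg, No AI (Section 4.1 gives 1 mg if symptoms) |
| Second | 400 (earlier sample 150 or 300) | no | 2.5 mg, No AI |
| Second | 400 (earlier sample 150 or 300) | yes | 2.5 mg, No AI **and** 1 mg, Partial AI |
| Fourth | 400 (earlier sample 150 or 300) | yes | 1 mg, No AI **and** 1 mg, Partial AI |

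The condition of at least 250 nmol/L in the Partial AI row is met by the same 400 nmol/L sample. All combinations tried with the later sample at 150 or 300 nmol/L satisfied exactly one row.

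**2. First-test timing.** Inputs are Protocol Table 7, a cortisol test after 4 weeks at 5 mg, and stability defined as 2 weeks without a dose change (Protocol Table 13, SAP Table 4). Assumptions are a first cut at Week 4, no asthma event, and a lag of L weeks from test to next cut, which the protocol does not state.

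- At 2.5 mg: 5 → 2.5 → 0, two cuts, so zero falls at test week + L + 4.
- At 1 mg: 5 → 4 → 3 → 2 → 1 → 0, five cuts, so zero falls at test week + L + 16.
- The gap is 16 − 4 = 12 weeks.
- To count as discontinued at Week 28, zero must be reached by Week 28 − 2 = Week 26.

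| Baseline dose | 5 mg reached (Week) | Test (Week) | Zero, L = 0: fast / slow | Zero, L = 4: fast / slow |
|---|---|---|---|---|
| 5 mg | at baseline | 4 | 8 / 20 | 12 / 24 |
| 7.5 mg | 4 | 8 | 12 / 24 | 16 / 28 |
| 10 mg | 8 | 12 | 16 / 28 | 20 / 32 |
| 20 mg | 12 | 16 | 20 / 32 | 24 / 36 |
| 30 mg | 15 | 19 | 23 / 35 | 27 / 39 |
| 40 mg | 17 | 21 | 25 / 37 | 29 / 41 |

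Against Week 26:

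- **L = 0:** Week 28 status differs between speeds for 10, 20, 30 and 40 mg, and not for 5 or 7.5 mg.
- **L = 1:** the pattern is the same (40 mg: 26 / 38).
- **L = 2:** 40 mg misses at both speeds (27 / 39).
- **L = 4:** status differs for 7.5, 10 and 20 mg; 30 and 40 mg miss at both speeds.

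The latest zero is Week 41, before down-titration stops at Week 48, so Week 52 discontinuation is unaffected absent other delays. The ≤ 5 mg/day endpoint is unaffected because the test is done at 5 mg.

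**3. Second-test timing.** Let s be the week of the first cut.

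- No AI row: 2.5 mg at s, 0 mg at s + 4, no retest.
- Partial AI row: 4 mg at s, 3 mg at s + 4, retest at about s + 8. If that is normal, 0 mg at s + 8 (Table 7 footnote a, direct stop from 3 mg or less), or 0.5 mg at s + 8 and 0 mg at s + 12 (third-test row).

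The choice of row therefore moves zero by 8 − 4 = 4 to 12 − 4 = 8 weeks, and adds or removes a cortisol check.

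**The case against.** The strongest reply on the first test is that the rule exists elsewhere. Section 4.1 applies to every site and sends only indeterminate results to the alternative method, so a participant above 350 nmol/L never needs the substitute and stays under Section 4.1. Section 8.1.2 also lets any investigator slow to 1 mg every 4 weeks from 5 mg/day because of symptoms. Table 7 is equally silent on symptoms, and Section 8.2.1.1 has the same unconditional 2.5 mg step after a normal repeat test. These points stand, so the slower rule does reach Appendix M sites. But Section 8.1.2 is permissive, and Appendix M has its own first-test row above 350 nmol/L that states a different action. Section 8.2.1.1 limits its version of the rule to tetracosactide sites.

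On the second test, the symptom clause adds something only when cortisol is above 350 nmol/L, which suggests it was meant to override the No AI row. Section 8.2.1.2 has a similar overlap and also gives 1 mg steps and a repeat test on symptoms. That reading is plausible, and it is the safer one. It is not stated, and the fourth-test row above 350 nmol/L, which keeps symptomatic participants as No AI, points the other way.

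On analysis, the AI proportions are exploratory, the AI-status subgroup is descriptive and no hypothesis is tested. The SAP does not say whether AI class comes from the laboratory value or the site's row, so double classification is possible but not certain. One participant in 300 moves a proportion by 1/300 = 0.33 points, against a planned half-width of 5.8 points. This limits the statistical weight of the point but does not touch the safety argument.

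**Conclusion.** The concern holds. Appendix M's first-test row, followed as written, gives a faster taper than Section 4.1 requires for a participant with normal cortisol and AI symptoms. Its second-test rows assign that participant both speeds and both statuses. At the fourth test only the status and its consequences conflict. The third-test row is a consistency point.

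The size is 4 weeks instead of 16 from first cut to zero at the first test, and 4 to 8 weeks' difference at the second if the retest is normal. Among the primary estimates only Week 28 discontinuation can move, and for which baseline doses depends on the lag from test to cut. The timings assume a first cut at Week 4, no asthma event and an uninterrupted taper. The number of participants affected is not given and may be small. SAP 4.2.1.7 lists Poland, Bulgaria and Latvia as lacking the ACTH test, and these make up the whole Central/Eastern Europe region in SAP 4.1.1.1. Any effect would therefore concentrate in one level of the region and ACTH-access subgroups.

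The main reason to act is patient safety, and the correction is cheap.

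**What to change.** In Appendix M, add the fourth-test symptom wording ("or 1 mg every 4 weeks if signs or symptoms of AI are present") to the row above 350 nmol/L of the first test, and of the third test for consistency. Rewrite the second- and fourth-test rows so that they do not overlap: above 350 nmol/L with AI symptoms should have one speed (1 mg every 4 weeks), one status, and one stated rule on retesting and emergency-card education. The sponsor's endocrinology advisers should choose the status. Notify the sites that use Appendix M.

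The cost is wording in one appendix table and a site notice. No new procedure is needed; if Partial AI is chosen, the repeat cortisol already in that row applies.
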